1.4.4.1.5. Action Taken

Missing actions taken will remain missing and not be imputed.

1.4.4.2. Immunogenicity

No imputation of missing values and no search for outliers will be performed. LLOQ and ULOQ management will be performed as described in [Section 4.2.3.1](#).

1.5. Interim Analysis

This study will not include an early safety data review. However, participant safety will be continuously monitored by the Sponsor's internal safety review committee which includes safety signal detection at any time during the study.

A first statistical analysis of the immunogenicity and safety data collected up to V2 (Day 31) (Group 1) and V1 (Group 2), 5 years after priming dose in the MET51 study, will be performed once data are available and an interim database lock has been conducted. The interim study report (5-year report) will include immunogenicity data from hSBA and safety data collected up to V2 (Day 31) (Group 1) and V1 (Group 2), 5 years after priming dose in the MET51 study .

The study reports at 5 years and 10 years after priming dose may not include the rSBA immunogenicity data in case of delays with the rSBA testing. The rSBA data will be presented in that case in a CSR addendum at the time of availability. .

A final analysis (10-year report after priming dose) will be performed at the end of the study period.

1.6. Data Monitoring Committee (DMC)

Not applicable.

4. Complementary Information on Assessment Methods

Study assessments and procedures are detailed in Section 8 of the protocol. This section focusses on complementary/additional information not detailed in the protocol.

1.7. Complementary Information for Endpoint[s] Assessment Method[s]

1.8. Complementary Information on Derived Endpoints: Calculation Methods

1.8.1. Safety

1.8.1.1. Solicited Reactions

1.8.1.1.1. Daily Intensity

All daily records for solicited reactions will be derived into daily intensity according to the following classification: None, Grade 1, Grade 2, Grade 3, or Missing (Unknown).

For the derivation of daily intensities the following sequential steps will be applied:

- 1) Solicited reactions (except Fever/Pyrexia) with CRF presence recorded as “No” and with all daily records missing (Unknown) then all daily intensities will be derived as None.
- 2) For non-measurable solicited reactions, daily intensities will correspond to daily records reported in the clinical database. For measurable solicited reactions the daily measurements reported in the clinical database will be converted based upon the intensity scales defined in the protocol; this assumes a reaction that is too large to measure (non measurable, “NM”) is Grade 3. Note the intensity could be considered “None” (not a reaction) in the analysis despite being considered a reaction by the investigator (e.g., swelling measurement > 0 mm but < 25 mm in adults).

Note: The maximum intensity on the ongoing period is derived from the record of the maximum intensity/measurement after the end of the solicited period following the rule described above.

Table 4.1 :Solicited injection site reactions: terminology, definitions, and intensity scales – Children at V2 (Group 1)

CRB term (MedDRA lowest level term [LLT])	Injection site pain	Injection site erythema	Injection site swelling
DC term	Pain	Redness	Swelling
Definition	Pain either present spontaneously or when the injection site is touched or injected limb is mobilized	Presence of a redness including the approximate point of needle entry	Swelling at or near the injection site Swelling or edema is caused by a fluid infiltration in tissue or cavity and, depending on the space available for the fluid to disperse, swelling may be either soft (typically) or firm (less typical) to touch and thus can be best described by looking at the size of the swelling
Intensity scale*	
CRB:
 
Grade 1: Easily tolerated
 
Grade 2: Sufficiently discomforting to interfere with normal behavior or activities
 
Grade 3: Incapacitating, unable to perform usual activities
 
DC:
 
Grade 1: No interference with usual activities
 
Grade 2: Some interference with usual activities
 
Grade 3: Significant; prevents usual activities
	
Grade 1: > 0 to < 25 mm
 
Grade 2: ≥ 25 to < 50 mm
 
Grade 3: ≥ 50 mm
	
Grade 1: > 0 to < 25 mm
 
Grade 2: ≥ 25 to < 50 mm
 
Grade 3: ≥ 50 mm

Abbreviations: DC, diary card; MedDRA, Medical Dictionary for Regulatory Activities

* For the subjective reaction of pain, participants or parents/LARs will record the intensity level (Grade 1, 2, or 3) in the DC. For the measurable reactions of redness and swelling, they will record just the size of the reaction, and the classification as Grade 1, 2, or 3 will be assigned at the time of the statistical analysis.

Note: This table is to be used for Group 1 at V2.

Table 4.2 :Solicited injection site reactions: terminology, definitions, and intensity scales – Adolescents and adults aged ≥ 10 years at V4 (Group 1) and V3 (Group 2)

CRF term (MedDRA lowest level term [LLT])	Injection site pain	Injection site erythema	Injection site swelling
Diary card term	Pain	Redness	Swelling
Definition	Pain either present spontaneously or when the injection site is touched or injected limb is mobilized	Presence of a redness including the approximate point of needle entry	Swelling at or near the injection site Swelling or edema is caused by a fluid infiltration in tissue or cavity and, depending on the space available for the fluid to disperse, swelling may be either soft (typically) or firm (less typical) to touch and thus can be best described by looking at the size of the swelling
Intensity scale*	
CRF: Grade 1: A type of adverse event that is usually transient and may require only minimal treatment or therapeutic intervention. The event does not generally interfere with usual activities of daily living. Grade 2: A type of adverse event that is usually alleviated with additional therapeutic intervention. The event interferes with usual activities of daily living, causing discomfort but poses no significant or permanent risk of harm to the research participant. Grade 3: A type of adverse event that interrupts usual activities of daily living, or significantly affects clinical status, or may require intensive therapeutic intervention.
 
Diary card: Grade 1: No interference with activity Grade 2: Some interference with activity Grade 3: Significant; prevents daily activity
	
Grade 1: ≥ 25 to ≤ 50 mm Grade 2: ≥ 51 to ≤ 100 mm Grade 3: > 100 mm
	
Grade 1: ≥ 25 to ≤ 50 mm Grade 2: ≥ 51 to ≤ 100 mm Grade 3: > 100 mm

MedDRA: Medical Dictionary for Regulatory Activities

* For pain, the scale will be provided in the CRF and the intensity will be transcribed from the diary card. For other injection site reactions (erythema and swelling), the classification as Grades 1, 2, or 3 will be applied at the time of statistical analysis; the scale is provided for information purposes only. The actual size of the reaction will be reported in the CRF.

Note: This table is to be used for Group 1 at V4 and for Group 2 at V3.

Table 4.3 : Solicited systemic reactions: terminology, definitions, and intensity scales – Children 2 through 11 years of age, adolescents or adults ≥ 12 years of age

CRB term (MedDRA lowest level term [LLT])	Fever	Headache	Malaise	Myalgia
DC term	Temperature	Headache	Feeling unwell	Muscle aches and pains
Definition	Elevation of temperature to $\geq 38.0^{\circ}\text{C}$ ($\geq 100.4^{\circ}\text{F}$)	Pain or discomfort in the head or scalp. Does not include migraine.	General ill feeling. Malaise is a generalized feeling of discomfort, illness, or lack of well-being that can be associated with a disease state. It can be accompanied by a sensation of exhaustion or inadequate energy to accomplish usual activities.	Muscle aches and pains are common and can involve more than one muscle at the same time. Muscle pain can also involve the soft tissues that surround muscles. These structures, which are often referred to as connective tissues, include ligaments, tendons, and fascia (thick bands of tendons). Does not apply to muscle pain at the injection site which should be reported as injection site pain.
Intensity scale*	Grade 1: $\geq 38.0^{\circ}\text{C}$ to $\leq 38.4^{\circ}\text{C}$, or $\geq 100.4^{\circ}\text{F}$ to $\leq 101.1^{\circ}\text{F}$	CRB: Grade 1: A type of AE that is usually transient and may require only minimal treatment or therapeutic intervention. The event does not generally interfere with usual activities of daily living.	CRB: Grade 1: A type of AE that is usually transient and may require only minimal treatment or therapeutic intervention. The event does not generally interfere with usual activities of daily living.	CRB: Grade 1: A type of AE that is usually transient and may require only minimal treatment or therapeutic intervention. The event does not generally interfere with usual activities of daily living.

CRB term (MedDRA lowest level term [LLT])	Fever	Headache	Malaise	Myalgia
	
Grade 2: $\geq 38.5^{\circ}\text{C}$ to $\leq 38.9^{\circ}\text{C}$, or $\geq 101.2^{\circ}\text{F}$ to $\leq 102.0^{\circ}\text{F}$
 
Grade 3: $\geq 39.0^{\circ}\text{C}$ or $\geq 102.1^{\circ}\text{F}$
	
Grade 2: A type of AE that is usually alleviated with additional therapeutic intervention. The event interferes with usual activities of daily living, causing discomfort but poses no significant or permanent risk of harm to the research participant.
 
Grade 3: A type of AE that interrupts usual activities of daily living, or significantly affects clinical status, or may require intensive therapeutic intervention.
 
DC: Grade 1: No interference with usual activities Grade 2: Some interference with usual activities Grade 3: Significant; prevents usual activities
	
Grade 2: A type of AE that is usually alleviated with additional therapeutic intervention. The event interferes with usual activities of daily living, causing discomfort but poses no significant or permanent risk of harm to the research participant.
 
Grade 3: A type of AE that interrupts usual activities of daily living, or significantly affects clinical status, or may require intensive therapeutic intervention.
 
DC: Grade 1: No interference with usual activities Grade 2: Some interference with usual activities Grade 3: Significant; prevents usual activities
	
Grade 2: A type of AE that is usually alleviated with additional therapeutic intervention. The event interferes with usual activities of daily living, causing discomfort but poses no significant or permanent risk of harm to the research participant.
 
Grade 3: A type of AE that interrupts usual activities of daily living, or significantly affects clinical status, or may require intensive therapeutic intervention.
 
DC: Grade 1: No interference with usual activities Grade 2: Some interference with usual activities Grade 3: Significant; prevents usual activities

Abbreviations: DC, diary card; MedDRA, Medical Dictionary for Regulatory Activities

* For all reactions but fever, participants or parents/LARs will record the intensity level (Grade 1, 2, or 3) in the DC. For fever, they will record the body temperature, and the classification as Grade 1, 2, or 3 will be assigned at the time of the statistical analysis based on the unit used to measure the temperature and the intensity scale.

1.8.1.1.2. Maximum Intensity

Maximum overall intensity is derived from the daily intensities computed as described in [Section 1.8.1.1.1](#) is calculated as the maximum of the daily intensities over the period considered.

1.8.1.1.3. Presence

Presence is derived from the maximum overall intensity over the time period considered:

- None: No presence
- Grade 1, Grade 2, or Grade 3: Presence
- Missing or Unknown: Missing presence

Subjects with at least one non-missing presence for a specific endpoint will be included in the analysis. Conversely, those without a non-missing presence will not be included in the analysis of the endpoint.

The time period is displayed as D1-D4, D5-D8, D9 and later.

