8.3.2 Method of Detecting Adverse Events and Serious Adverse Events

Individual DCs, specifically designed for this study by the Sponsor and provided to the study sites, will be given to study participants' parents/LARs for the recording of daily safety information. These DCs will include pre-listed terms and intensity scales as well as areas for free text to capture additional safety information or other relevant details. Participants' parents/LARs will also be provided with rulers for measuring the size of injection site reactions, and with certified standard digital thermometers for measuring daily temperatures. To ensure consistency of reporting, the study sites will instruct participants' parents/LARs on how to correctly use these tools.

At specified intervals, the Investigator or an authorized designee will interview the participants' parents/LARs to collect the information recorded in the DC, and will attempt to clarify anything that is incomplete or unclear. All clinical study information gathered by the study site will be reported electronically by the Investigator or authorized designee using a web-based CRB. Any information that was not documented in the DC will first be captured in the source document and then reported electronically.

The method of recording, evaluating, and assessing causal relationship of AE and SAE and the procedures for completing and transmitting SAE reports are provided in [Appendix 10.2](#).

Care will be taken not to introduce bias when detecting AEs and/or SAEs. Open-ended and non-leading verbal questioning of the participants' parents/LARs is the preferred method to inquire about AE occurrences.

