1.4.4.1.3. Intensity

For solicited reactions, missing intensities will be handled as described in [Section 1.8.1.1.1](#). For unsolicited AEs, missing intensities will remain missing and will not be imputed.

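### For most solicited reactions, a participant recorded as having reacted but with no daily records is dropped from the rate, while the matching recorded non-reactor is kept

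*SAP*

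**What the plan says.** Four SAP rules act in sequence on a solicited reaction.

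- **SAP 1.8.1.1.1, step 1.** It covers reactions "with CRF presence recorded as “No” and with all daily records missing (Unknown) then all daily intensities will be derived as None". The step opens "Solicited reactions (except Fever/Pyrexia", so fever is outside it.
- **SAP 1.8.1.1.1, step 2.** "For non-measurable solicited reactions, daily intensities will correspond to daily records reported in the clinical database". Measurable reactions are graded from the recorded measurements. Neither part of the step mentions the CRF presence field.
- **SAP 1.8.1.1.2.** Maximum intensity is the largest of the daily intensities.
- **SAP 1.8.1.1.3.** "Presence is derived from the maximum overall intensity over the time period considered". A missing maximum gives missing presence, and then: "Conversely, those without a non-missing presence will not be included in the analysis of the endpoint".

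The section on missing data, SAP 1.4.4.1.3, adds no further rule: "For solicited reactions, missing intensities will be handled as described in" SAP 1.8.1.1.1, which is the section above.

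Protocol 8.3.2 describes one way in which presence could be known without a complete diary. The site interviews the parent and tries to resolve gaps, and "Any information that was not documented in the DC will first be captured in the source document and then reported electronically".

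**The concern.** The same CRF field is used when it reads No and ignored when it reads Yes. Two participants with the same gap in daily data are treated differently according to the answer on record. The non-reactor stays in the denominator, and the reactor disappears from the endpoint.

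Solicited injection site and systemic reactions are one of the listed endpoints for all three safety objectives: the 5-year booster in Group 1, the 10-year booster in Group 2 and the second booster in Group 1. A rule that removes known reactors understates the rates reported for them.

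It also departs from how the SAP treats incomplete safety records elsewhere:

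- An unsolicited event needs only a verbatim term and a grade other than 0, so one with missing intensity still counts (SAP 1.8.1.2.1).
- A missing causality assessment for an unsolicited systemic event is taken as related (SAP 1.4.4.1.2).
- A reaction too large to measure is Grade 3 (SAP 1.8.1.1.1).
- Among events leading to discontinuation, an unsolicited event counts if its grade is missing, but a solicited one must be at least Grade 1 (SAP 1.8.2.6).

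**Working it through.** The documents state no expected reaction rate, missing-diary rate or safety precision target, so there is no figure of the plan's own to reproduce. The check traces the rules and then uses algebra.

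**Tracing one participant with no daily records**

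| CRF presence | Daily intensities | Maximum | Presence | In the analysis? |
|---|---|---|---|---|
| No (not fever) | None (step 1) | None | No presence | Yes, as a non-reactor |
| Yes | Missing (step 2) | Missing | Missing | No |
| Fever, either answer | Missing | Missing | Missing | No |

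The Yes row is inferred from the absence of a rule together with SAP 1.8.1.1.3; the SAP does not state it. A maximum intensity recorded after the solicited period could still register under the D9-and-later display.

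**Which reactions are affected in a known direction**

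The direction is fixed where Yes must mean at least Grade 1. That holds for pain (SAP Tables 4.1 and 4.2) and for headache, malaise and myalgia (Table 4.3), where the lowest grade is a reaction without interference. It also holds for erythema and swelling at the first booster, graded from above 0 mm (Table 4.1).

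**Algebra for those reactions**

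Let M be participants with daily data, R the reactors among them, a the participants with No and no daily records, and b those with Yes and no daily records.

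- SAP rate = R / (M + a)
- Rate counting every recorded reactor = (R + b) / (M + a + b)
- Difference = b(M + a − R) / [(M + a)(M + a + b)]

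The difference is never negative. It is positive whenever b > 0, unless everyone else counted also reacted. It is zero when b = 0.

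**Size under assumed values**

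N = M + a + b = 250 is the maximum estimate per group in SAP 1.2. The true rate and the share of reactors with Yes and no daily record are assumptions. With T = R + b true reactors, the SAP rate is (T − b) / (N − b). For example, at a true rate of 30% with 10% of reactors affected, T = 75 and b = 7.5, so the rate is 67.5 / 242.5 = 27.84%.

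| True rate | 1% of reactors affected | 5% | 10% |
|---|---|---|---|
| 10% | 9.91% | 9.55% | 9.09% |
| 30% | 29.79% | 28.93% | 27.84% |
| 50% | 49.75% | 48.72% | 47.37% |

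The shortfall runs from 10 − 9.91 = 0.09 to 50 − 47.37 = 2.63 percentage points. In whole participants, with 100 reactors of 250 (40.0%) of whom 5 have Yes and no daily record, the SAP rate is 95 / 245 = 38.8%.

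**Where the direction is not fixed**

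- *Fever.* Both answers are dropped. Take 10 true cases of 250 (4.0%). Dropping 10 No gives 10 / 240 = 4.17%. Dropping 10 No and 1 Yes gives 9 / 239 = 3.77%. Dropping 25 No and 1 Yes gives 9 / 224 = 4.02%.
- *Year 5 erythema and swelling.* Grading starts at 25 mm (Table 4.2), and SAP 1.8.1.1.1 itself notes that a smaller reaction becomes None. Take 25 true of 250 (10.0%) and 5 Yes without a size. The SAP rate is 25 / 245 = 10.2% if none of the five reached 25 mm and 20 / 245 = 8.2% if all did.

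**The case against.** The case against has five parts.

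1. **Such participants may hardly exist.** Under Protocol 8.3.2 sites interview parents and try to resolve whatever is incomplete. That can recover grades and sizes as well as a bare Yes or No. The call 8 to 10 days after vaccination also reminds parents to keep using the diary. This stands: the procedure should keep the number low. Step 1 nevertheless shows that the SAP foresees a presence answer without daily records.
2. **A blank grid after No may be complete information.** The CRF may leave the daily fields empty once No is entered; the documents neither confirm nor exclude this. This also stands. The rule for No uses recorded information and is not itself a fault. The fault is not using a Yes in the same way.
3. **The effect is small against sampling error.** At 40% and n = 250 the 95% half-width is about 1.96 × √(0.4 × 0.6 / 250) = 6.1 points, and safety is descriptive. True, but the confidence interval does not cover a systematic loss of known reactors.
4. **The SAP generally does not replace missing safety data.** Counting a Yes as present imputes no grade; it uses an answer already in the database.
5. **The safety objectives do not rest on solicited reactions alone.** Immediate events, unsolicited events and serious events also contribute, and are unaffected.

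A reader might infer that every solicited rate is biased downward, or that bare Yes or No answers are to be expected in a sizeable share of participants. The documents support neither. Fever is exempt from step 1, Year 5 erythema and swelling can move either way, and no frequency is given.

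**Conclusion.** The point holds in a limited form. Followed exactly, the SAP keeps a recorded non-reactor and discards a recorded reactor when neither has daily records. For pain, headache, malaise and myalgia after any booster, and for erythema and swelling after the first booster, this understates the reported rate whenever such a reactor exists.

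The size is unknown. The range of about 0.1 to 2.6 percentage points rests on the assumed shares and rates in the table, and on taking a CRF Yes as correct and as referring to the solicited period. No direction can be claimed for fever or for Year 5 erythema and swelling. The primary immunogenicity objective is unaffected. The rule is worth correcting because it discards information already held, and a choice made after the data are seen would be harder to defend.

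**What to change.** - **Listed reactions.** Add to SAP 1.8.1.1.1 and 1.8.1.1.3 that CRF presence Yes with all daily records missing is counted as present with intensity Missing. The participant enters the numerator and denominator of any reaction and appears on a grade-missing line in the maximum-intensity table.
- **Year 5 erythema and swelling.** Keep No as None. Report how many participants have Yes without a measurement, and show the rate both ways: all of them None, and all of them at least Grade 1. Setting No without measurements to missing for symmetry would be wrong, because No is None on any size scale. For illustration, with 25 true reactors of 250 (10%) and an assumed 150 of the 225 non-reactors recorded as No with no measurements, removing those 150 would give 25 / 100 = 25%.

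The cost is one SAP sentence and a small change to the derivation code for the listed reactions, one extra table line, the two-way display for Year 5 erythema and swelling, and possibly slightly higher reported rates. No new data are needed.

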1.8.1.1.4. Time of Onset

Time of onset is derived from the daily intensities computed as described in [Section 1.8.1.1.1](#). It corresponds to the first day with intensity of Grade 1, Grade 2, or Grade 3.

Note: If a reaction is not continuous (i.e., reaction occurs over two separate periods of time intervened by at least one daily intensity Missing or None) then the time of onset is the first day of the first occurrence.

Time of onset period is displayed as, D1-D4, D5-D8.

1.8.1.1.5. Number of Days of Occurrence During the Solicited Period

Number of days of occurrence over the period considered is derived from the daily intensities computed as described in [Section 1.8.1.1.1](#). It corresponds to the number of days with daily intensities of Grade 1, Grade 2, or Grade 3. Number of days of presence on the solicited period with a specified intensity may also be derived.

